6.7 Adverse Events

For patients on the treatment arm Pre-treatment AE's will be defined as those where "Did this AE start prior to first dose of IMP?" is ticked. Treatment Emergent AE's will be defined as those where "Did this AE start prior to first dose of IMP?" is not ticked. For patients on the control arm pre-treatment AE's will be defined as those where the AE started prior to Day 1. Treatment emergent AE's will be defined as those where the AE started after and inclusive of Day 1.

Treatment related AE's are those where causality to IMP is considered to be Possible, Probable or Highly Probable.

COVID-19 related AE's will be defined as those where "Is this AE related to COVID-19" is ticked yes.

The frequency of AEs will be summarised overall and by treatment arm. A patient can be counted multiple times per row for the No. of Episodes but will only be counted once per row for the No. of Patients.

Table 5: Frequency of All Adverse Events

Safety population

MedDRA System Organ Class (SOC) MedDRA Preferred Term	No. of Episodes Reported	No. of Patients N=XX	No. of Patients in Treatment Arm N=XX	No. of Patients in Control Arm N=XX
All AE's	N	N (%)	N (%)	N (%)
BLOOD AND LYMPHATIC...				
Anemia				
CARDIAC DISORDERS				
Sinus tachycardia				
Etc				

There will be additional versions of the above table based on pre-treatment AE's, treatment emergent AE's, treatment emergent SAE's (any AE that is considered Serious), related treatment emergent AE's. COVID-19 related AE's.

Overview of treatment emergent adverse events (by treatment arm). An AE is considered to have led to withdrawal if an adverse event with "Did the AE cause the subject to be discontinued from the study?" is recorded as yes.

Table 6: Overview of Treatment Emergent Adverse Events (Inclusive and post Day 1)

Safety population

Patients with TEAEs	Overall No. of Patients N=XX	No. of Patients in Treatment arm N=XX	No. of Patients in Control arm N=XX
Patients with >=1 TEAE	N (%)	N (%)	N (%)
Patients with >= 1 TE SAE			
Patients with >= 1 COVID-19 related			
Patients with >= 1 Treatment related			
Patients with >= 1 AE leading to withdrawal			
Patients who died			

Treatment emergent adverse events leading to withdrawal of treatment will be listed by patient. Patients will be included if an adverse event has "Action taken" recorded as "Drug Withdrawn" or "Did the AE cause the subject to be discontinued from the study?" is recorded as yes.

Table 7: Breakdown of TEAEs leading to Patient withdrawal.

Safety population

Patient number	MedDRA System Organ Class (SOC)	AE Term	Serious	Led to IMP withdrawal	Led to withdrawal from study

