7.2.4 Dispensing of camostat

Sufficient tablets of camostat must be dispensed on each occasion to cover the prescribed dose for the full treatment period i.e. Days 1-14.

Patients should be supplied with the required quantity of camostat in the original boxes to cover the prescribed dose. Blister packs must not be cut to reduce tablet numbers at dispensing.

The tablets are supplied in blister packs and must not be removed from the primary packaging (provided to the patient) and placed in any other container. Tablets should be stored at room temperature and out of sight and reach of children.

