Assessment ⁶	Testing site	Home (or at site if permitted)	Home visit	Daily video call (or phone)	Home visit (or at site if permitted)	Daily call	Home visit (or at site if permitted)	Video call (or phone)	Video call (or phone)
Blood (FBC& U&Es & other markers)							■		
Blood - PK		X							
Pregnancy test for women of childbearing potential									
Demographics		X							
▪ Height, weight									
▪ Medical history									
▪ Risk factors									
▪ COVID-19 symptoms check									
▪ COVID-age risk									
Delivery of camostat ^c				X					
Camostat administration ^E				X					
				X					
				(first dose)					
					X				
					(if patient recovered, discontinue camostat)				
Documentation of supplementary oxygen administration/ high-flow oxygen device						X			
Assessment of:		X				X		X	
▪ ordinal scale status assessment									
Call with clinical researcher				X		X		X	X

A. The intention is that home visits, by a clinical professional, occur on Days 7 and 14 to take research bloods, PK bloods and repeat swab. However, this requirement may change if patients are permitted to provide samples by visiting the site. If the Sponsor and site decide that sampling is not required, this will be communicated to the patient. The Day 7 and 14 video (phone) calls will still go ahead as planned regardless of sampling.

■

C. If randomised to the camostat arm, patients will also receive camostat tablets to last for 14 days.

D. Two readings a day.

E. Trial packs and, for those patients randomised to the treatment arm, camostat may be delivered by courier or site staff.

■

G. For community patients, home visits can be performed on site if permitted by government guidance. **For hospital based patients these assessments may be performed face to face, if feasible.**

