6.10 General data conventions

Data will be grouped according to the assigned treatment arm, as specified in the study protocol. Patients who deviate from the assigned treatment arm will be clearly described in the CSR with regards to their treatment modification and if applicable in the list of protocol deviations (Section 5.2).

Continuous variables will be summarised and presented with summary statistics.

Categorical variables will be summarised in frequency tables. Percentages in the summary tables will be rounded and may therefore not always add up to exactly 100%.

The convention in Rave is that an unknown day resolves to 1st of the month and an unknown month resolves to January. Dates may be ordered by this, however CRUK do not perform calculations on unknown dates.

Durations of AEs: the start date of an AE is considered as Day 1 of the event and should be included in all duration calculations (i.e. if an AE starts and stops on same day, the duration should be reported as one day).

- For unrelated AEs, those with missing or partially completed end dates will not be excluded from analysis and the duration of the AE will remain as unknown.
- For related AEs, prior to final data lock, an end date will be either i) confirmed AE end date or ii) stabilisation of AE. If lost to follow-up then the AE would stay as not recovered/not resolved. In both these cases duration would not be calculated.

Time to onset of AEs from IMP administration: the time to onset should be calculated from the date of the first administration of IMP in the trial (e.g. Day 1). Onset time will be calculated as 0 if the AE occurs on the same day as the dose.

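### Treatment-emergent AEs start at first dose on camostat but at calendar Day 1 in controls, so the by-arm TEAE tables classify the same Day 1 event differently

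*SAP*

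**What the plan says.** The rules stand together in RAP section 6.7 (in the SAP document).

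- Camostat arm, before treatment: "For patients on the treatment arm Pre-treatment AE's will be defined as those where" a case-report question about onset before the first dose is ticked. Its counterpart is "Treatment Emergent AE's will be defined as those where 'Did this AE start prior to first dose of IMP?' is not ticked", so a blank counts as emergent.
- Control arm, before treatment: "For patients on the control arm pre-treatment AE's will be defined as those where the AE started prior to Day 1". Its counterpart is "Treatment emergent AE's will be defined as those where the AE started after and inclusive of Day 1".
- The overview table carries one window for both arms: "Table 6: Overview of Treatment Emergent Adverse Events (Inclusive and post Day 1").

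On what Day 1 is, RAP section 6.10 says of AE timing that "the time to onset should be calculated from the date of the first administration of IMP in the trial (e.g. Day 1"), which points to the first-dose date on camostat. Protocol section 7.2.4 agrees, asking for enough tablets "to cover the prescribed dose for the full treatment period i.e. Days 1-14". Controls take no study drug. RAP section 7.2 uses Day 1 as the milestone for having started, but nothing says which event sets it for them. Table 1 of the Protocol gives Day 1 its own column, apart from screening and randomisation, and a note to it says that "camostat may be delivered by courier or site staff".

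**The concern.** A by-arm comparison of event counts needs the same observation window in both arms. Here the window opens at the first tablet in one arm and at the start of a calendar day in the other. On a common Day 1, the control window is never the shorter one.

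The early hours are not empty. Patients must be symptomatic to enter (Protocol 6.1), and AEs are recorded from consent in both arms (Protocol 12.3), so events before the first dose will be captured and must be classified. Time from randomisation to first dose will also vary: Emergency Department patients get their pack in the department (Protocol 9.1.2), while others have it delivered.

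The tables are read without a test, because Protocol 13.1 plans none. Readers will compare the columns directly, and a larger sample would not remove a difference that comes from the definition. Of the eight AE tables listed in RAP 8.2, seven rest on the split between pre-treatment and treatment-emergent events; the all-AE table does not.

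**Working it through.** The plan gives no figure on this point, so there is none to reproduce. The check has two parts: how one event is classified, and how much the window difference could move a proportion.

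**Classification.** Take an AE that begins on Day 1.

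| Onset on Day 1 | Camostat, RAP 6.7 rule | Control, RAP 6.7 rule | Table 6 title |
|---|---|---|---|
| Before the hour of first dose | Pre-treatment (if ticked) | Treatment emergent | Treatment emergent |
| After the hour of first dose | Treatment emergent | Treatment emergent | Treatment emergent |

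The first row differs by arm, and its camostat entry also disagrees with the table title.

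**Window length.** Let g be the time from the start of control Day 1 to the first dose. Follow-up ends 28 days from Day 1 in both arms (Protocol 12.3), so the windows are 28 days in controls and 28 − g on camostat. If Day 1 is the first-dose date, g is under 1 day, which is under 1/28 = 3.6% of the window.

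**Effect on the proportion with at least one TEAE.** The documents give neither g, nor the TEAE proportion P, nor the shape of the hazard. These are assumptions, shown as ranges. Both arms are given the same true hazard, so any difference is artefact. With L = −ln(1 − P):

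- constant hazard over 28 days: artefact = (1 − P) × [exp(gL/28) − 1]
- front-loaded, with half of the cumulative hazard spread evenly over the first 3 days: artefact = (1 − P) × [exp(gL/6) − 1], for g up to 3 days

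For P = 0.5, L = 0.693. At g = 1 day:

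- constant: 0.5 × [exp(0.0248) − 1] = 0.0125, or 1.3 points
- front-loaded: 0.5 × [exp(0.1155) − 1] = 0.061, or 6.1 points

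Control excess in percentage points at P = 50%, with the range for P from 30% to 70% in brackets:

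| g (days) | Constant hazard | Front-loaded |
|---|---|---|
| 0.25 | 0.3 (0.2 to 0.3) | 1.5 (1.0 to 1.5) |
| 0.5 | 0.6 (0.4 to 0.7) | 3.0 (2.1 to 3.2) |
| 1 | 1.3 (0.9 to 1.3) | 6.1 (4.3 to 6.7) |
| 2 | 2.5 (1.8 to 2.7) | 13.0 (8.8 to 14.8) |

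The last row applies only if control Day 1 is set at randomisation and dosing follows two days later.

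**Yardstick.** With 50 per arm and 50% in each, the standard error of the difference is √(2 × 0.25/50) = 0.10, or 10 points. With one start rule in both arms, the artefact is 0.

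**The case against.** The case against rests on scope, size and direction, and much of it stands.

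- **Scope.** A reader might infer that the primary outcome itself is biased. The documents do not support that. Protocol 13.1 and SAP appendix section 12 define it as AEs and their severity, with no restriction to TEAEs. Table 5 in its all-AE version is by arm and unfiltered. The registry primary measure (RAP 7.4) has no TEAE filter, and a separate pre-treatment table keeps pre-dose camostat events visible.
- **Length of the gap.** A reader might infer that late courier delivery stretches the gap to days. That needs control Day 1 to be fixed at randomisation, which no section states. If camostat Day 1 is the first-dose date, late delivery moves Day 1 along with the dose. The delivery note shows why Day 1 should be defined; it does not prove a long gap.
- **Size.** One might multiply an assumed share of patients with a first AE on Day 1 by the fraction of that day before dosing: 10% times a quarter to a half gives 2.5 to 5 points. This is an upper bound as well as an assumption, because a patient with any later TEAE still counts in Table 6. Being symptomatic at entry does not by itself show that new AEs cluster on Day 1.
- **Direction.** A reader might infer that the rule flatters camostat. Two features push the other way. A box left blank turns a camostat event into a TEAE. Controls must complete Day 1 to enter the safety population (RAP 5.1), so those who leave that day take their AEs with them, while a camostat patient needs only one dose.

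None of this removes the core fact that one table uses two rules. That differences are reported only to inform later trials lowers the stakes, but it is no reason to keep an avoidable mismatch.

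**Conclusion.** The point holds in a limited form. RAP 6.7 classifies AEs as treatment emergent by different rules in the two arms, and the Table 6 title does not match the camostat rule. Table 6 and the treatment-emergent versions of Table 5 are affected.

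On the reading that Day 1 is the first-dose date, the extra control window is under one day and the likely artefact is small against a 10-point standard error: about 0.6 to 1.3 points under constant hazard, or 3.0 to 6.1 if front-loaded, for gaps of 0.5 to 1 day with 50% of controls having a TEAE. These figures isolate the window effect. They leave out blank boxes and the Day 1 completion rule, so the net direction in counts remains open. The point merits correction because the mismatch is written into the plan and is cheap to remove.

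**What to change.** 1. State what sets Day 1 in each arm, including the event that sets it for controls.
2. In every by-arm TEAE table, count AEs with onset date on or after calendar Day 1 in both arms, and make the RAP 6.7 text and the Table 6 title say so.
3. Keep the flag for onset before first dose for the camostat-related AE tables, or as a sensitivity analysis.

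Calendar Day 1 is the practical choice. Starting at the date and time of randomisation would need AE onset times, and Protocol 12.3 lists only the onset date.

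The cost is a RAP edit and one derived flag, with no new data once Day 1 is defined. A few Day 1 events from before the first dose will enter the camostat column, which is the small price of treating both arms alike. The rule also needs a line on incomplete onset dates, since RAP 6.10 makes no calculations on unknown dates.

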12.3 Procedures for Recording Adverse Events

All AEs will be recorded in the eCRF.

The following information will be recorded: patient ID including the patient trial number, age and gender; verbatim term for the AE description, date of onset and end date as well as outcome, severity of the event, assessment of relatedness to trial medication, other suspect drug or device and action taken. Follow-up information should be provided as necessary. AEs should be recorded on the CRF from the date of written/verbal informed consent (whichever is the earlier) being given until they have completed the 28 days from Day 1 follow up period.

AEs considered related to the trial medication or COVID-19, as judged by a medically qualified investigator or the sponsor will be followed until resolution or the event is considered stable. All related AEs that result in a patient's withdrawal from the trial or are present at the end of the trial, should be followed up until a satisfactory resolution occurs.

It will be left to the investigator's clinical judgment whether or not an AE is of sufficient severity to require the patient's removal from treatment. Although the Sponsor will hold the final decision if there is a disagreement in the management of the patient's treatment. A patient may also voluntarily withdraw from treatment due to what he or she perceives as an intolerable AE. If either of these occurs, the patient must undergo an end of study assessment and be given appropriate care under medical supervision until symptoms of the AEs cease or the condition becomes stable.

The severity of events will be assessed on the following scale: 1 = mild, 2 = moderate, 3 = severe and as judged by a medically qualified investigator.

For hospitalised patients who are admitted (for any reason other than COVID-19) and subsequently test positive for COVID-19, medical occurrences or symptoms of deterioration that are expected as a consequence of the participant's admission hospital should be recorded in the patient's medical notes and only be reported as AEs in the eCRF if medically judged to have unexpectedly worsened during the study. AEs considered related to the trial medication or COVID-19, as judged by a medically qualified investigator or the sponsor will be reported in the eCRF.

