8.2 TABLES

Demographic Data

Baseline characteristics by treatment arm

Reasons for patient withdrawal / completion

Compliance

Treatment modifications and/or non-compliance (treatment arm only)

Efficacy Data

Ordinal Scale

Summary of Secondary Endpoint Data

Safety Data

Overview of Treatment Emergent Adverse Events (Inclusive and post Day 1)

Frequency of All Adverse Events

Frequency of pre-treatment AEs

Frequency of TEAEs

Frequency of All Camostat related treatment emergent AEs

Frequency of all COVID-19 related treatment emergent AEs

Frequency of all treatment emergent SAEs

Breakdown of TEAEs leading to Patient withdrawal

Neutrophils:Lymphocytes ratio per patient (treatment and control arm respectively)

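### Treatment-emergent status rests on AE start alone, so an AE that began between consent and first dose or Day 1 and later worsened or became serious can be missing from the treatment-emergent tables

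*SAP*

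**What the plan says.** The treatment-emergent rule is in section 6.7 of the Reporting Analysis Plan (RAP), to which the SAP is an appendix. It differs by arm but has the same form in both.

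- Camostat arm: a tick box on the AE form. "Treatment Emergent AE's will be defined as those where 'Did this AE start prior to first dose of IMP?' is not ticked".
- Control arm: start relative to Day 1. "Treatment emergent AE's will be defined as those where the AE started after and inclusive of Day 1".

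Collection begins earlier than either anchor. Protocol 12.3 says: "AEs should be recorded on the CRF from the date of written/verbal informed consent (whichever is the earlier) being given".

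RAP 6.7 first sets out "Table 5: Frequency of All Adverse Events", by arm and without a treatment-emergent restriction. It then promises further versions, including a pre-treatment one and one for "treatment emergent SAE's (any AE that is considered Serious"). The table list in RAP 8.2 names one SAE frequency table, "Frequency of all treatment emergent SAEs", and one camostat-related frequency table, also limited to treatment-emergent events. RAP 6.6 says, without that limit, that SAEs will be tabulated.

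The primary endpoint is the causality and severity of each AE. SAP appendix sections 10 and 12 describe it through AEs by worst severity and relatedness, compared between arms, with no restriction to treatment-emergent events.

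**The concern.** A treatment-emergent table is meant to show what happened once treatment, or the matching control period, had begun. An event that was mild before first dose and became severe or serious afterwards belongs there. A rule based only on start places it before treatment.

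The design leaves room for such events. For community patients, blood tests, eligibility review, randomisation and pack delivery (possibly by courier) all follow consent. Protocol 12.1.1 allows an abnormal laboratory finding to be an AE. Protocol 6.2 admits patients with ALT or AST raised to just under 2.5 times the upper limit of normal. Protocol 12.6 lists liver enzyme changes as events of interest. If a raised value at screening were recorded as an AE and then rose sharply on camostat, it would still carry a pre-treatment start.

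At stake is how far a reader can rely on the SAE and camostat-related tables in a trial whose primary endpoint is AE causality and severity. Using one anchor for both arms would not cure this, because the gap is the missing worsening criterion.

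**Working it through.** **Inputs.** Treatment-emergent rules, Table 5 and its versions, Tables 6 and 7: RAP 6.7. Table list: RAP 8.2. AE recording from consent: Protocol 12.3. Causality definitions: Protocol 12.2. Registry tables: RAP 7.3 and 7.4. Up to 50 patients per arm: RAP section 4. The plan has no figure of its own here. The sample size concerns the recruitment rate, and the AE comparison is descriptive.

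**Step 1. Is there a worsening rule elsewhere?** Only in Protocol 12.3, for patients recruited in hospital. It says when an expected deterioration should be reported as an AE, but not what start date it takes. Neither document says whether a worsening stays on the original AE record or becomes a new one.

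**Step 2. Trace one event under both conventions.** Take dyspnoea that starts after consent but before first dose or Day 1, and leads to admission as an SAE on Day 4.

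| Output | Worsening kept on original record | Worsening entered as new AE |
|---|---|---|
| Table 5, all AEs by arm | counted | counted |
| Pre-treatment version | counted | original event only |
| TEAE and treatment-emergent SAE versions | absent | counted |
| Table 6, TEAE and SAE rows | absent | counted |
| Camostat-related treatment-emergent version | absent | counted if judged related |
| COVID-19-related version, as listed in RAP 8.2 | absent | counted if so marked |
| Table 7, TEAEs leading to withdrawal | absent | counted if it led to withdrawal |
| AE listings | shown | shown |
| Registry SAE table (RAP 7.3) | counted | counted |

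The loss therefore occurs only under the first convention.

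**Step 3. What do the unrestricted tables show?** Table 5 has columns for episodes and patients, but none for severity, seriousness or relatedness. The SAP appendix promises tables by worst severity and relatedness, yet RAP 8.2 lists no severity table. The registry primary measures in RAP 7.4 are worded for AEs over Days 1 to 28 and do not say whether an event that started earlier counts.

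**Step 4. Causality.** Under Protocol 12.2, each of the three grades that count as drug-related requires a start plausibly timed to dosing. Read literally, a record with a pre-dose start would not qualify. A change to RAP 6.7 alone might therefore not bring the event into the camostat-related table.

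**Step 5. Size.** One patient in an arm of 50 is 1/50 = 2.0 percentage points of a Table 6 row, provided the patient has no other event that qualifies for that row. The share q of patients affected is not in the documents. For assumed values, the expected number per arm is 50q and the chance of at least one in an arm is 1 − (1 − q)^50:

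| Assumed q | Expected per arm | Chance of at least one in an arm |
|---|---|---|
| 1% | 0.5 | 39% |
| 2% | 1 | 64% |
| 5% | 2.5 | 92% |
| 10% | 5 | 99% |

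**The case against.** The strongest reply is that nothing leaves the primary safety analysis. A reader might infer that these events drop out of the primary safety tables, or that SAEs vanish from the report. The documents do not support that. The primary outcome is worded for AEs and SAEs in general, and a tabulation by worst severity would count a worsened event at its worst grade. Table 5, the pre-treatment table and the listings keep the event. So does the registry SAE table, although RAP section 7 reserves that for upload and not for the study report. An admission for COVID-19 in a community patient also counts in the hospitalisation endpoint, subject to the efficacy population.

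Three further points carry weight.

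- The loss depends on a recording convention that the documents do not give. If sites enter a worsening as a new AE, the present rule already works.
- Symptoms present at entry are collected as baseline data, so that every patient is symptomatic does not by itself create affected records. Only onsets between consent and first dose or Day 1 matter, and that gap may be short for patients randomised in an emergency department.
- A patient with another TEAE is still counted in Table 6, so the number of affected events overstates the shift.

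These points limit the scope and size of the concern. They do not supply the missing criterion, and they leave RAP 8.2 with no SAE or camostat-related frequency table free of the restriction.

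**Conclusion.** The point holds in limited form. The definition uses start alone in both arms. If worsening is kept on the original record, an AE that began between consent and first dose or Day 1 and then worsened or became serious is presented as pre-treatment. It is then absent from the TEAE table, Tables 6 and 7, and the only SAE and camostat-related frequency tables listed in RAP 8.2. It is misclassified but still visible elsewhere.

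The number of patients affected cannot be derived from the documents. The only firm figure is 2 percentage points of a Table 6 row per affected patient, at 50 per arm and with no other qualifying event. RAP 6.6 and RAP 8.2 also disagree on whether SAEs are tabulated in full. The change is worth making because these tables serve the primary endpoint and the remedy is cheap.

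**What to change.** 1. In RAP 6.7, define treatment-emergent in both arms as an AE that started, increased in severity or became serious on or after first dose (camostat) or Day 1 (control).
2. State in the eCRF completion guidance that a worsening after that point is entered as a new AE line with its own onset date. Causality under Protocol 12.2 can then be judged on the worsening.
3. Produce the treatment-emergent versions of Table 5, and Tables 6 and 7, on this definition. The base Table 5 keeps its all-AE scope.
4. Reconcile RAP 6.6 with RAP 8.2. Listing an all-SAE frequency table beside the treatment-emergent one would do this.

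The cost is RAP wording, a short eCRF note and some queries to date worsening in existing records.
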